4.3 Study Treatments

The investigational products in this study are 200 mg CSL312 and placebo.

Subjects randomized to the Active Arm will receive CSL312 SC once a month for 6 months. The first dose of CSL312 will be a 400 mg loading dose administered subcutaneously on the same day as 2 separate injections at the study site (ie, Month 1). Subsequent doses of CSL312 will be 200 mg administered SC once monthly for 5 consecutive months (ie, Months 2 through 6).

Subjects randomized to the Placebo Arm will receive volume-matched placebo once monthly for 6 months. The first dose of placebo in the Placebo Arm will be volume-matched (400mg loading dose) placebo administered SC as 2 separate injections (ie, Month 1). Subjects will then receive volume-matched placebo SC once a month for 5 consecutive months (ie, Months 2 through 6).

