9.2 Protocol Deviations

All identified protocol deviations throughout the study will be listed prior to database lock and will be classified into minor/major by CSL. Major protocol deviations are defined as deviations that could have a significant effect on the subject's safety, rights, or welfare and/or on the integrity of the study data.

The protocol deviations' classification into minor and major will be reassessed under statistical considerations. During the blinded data review meeting (BDRM), the classification and the subject's assignment to any analysis set will be discussed in detail. The decisions made during the BDRM will be documented in the BDRM minutes and agreed upon prior to database lock for final analysis.

Table 9 Potential Protocol Deviations

Potential Protocol Deviations	Potential Exclusion From Analysis Set
Subject did not provide informed consent and/or informed consent date missing	Screening, SAF, ITT, PP, PK, PD
Subject randomized but not treated with study treatment	SAF, PP, PK, PD
Subjects treated with incorrect study treatment	PP, PK, PD
Subject randomized and treated but does not have at least one measurable PK concentration	PK
Subject randomized and treated but does not have at least one PD measurement	PD
Subject randomized and treated but without primary efficacy assessment	PP
Subject randomized and treated but violated inclusion and/or exclusion criteria	PP, (SAF, ITT, PK, PD)
Subject randomized and treated but compliance outside 80-120%	PP, (PK, PD)
Subject randomized and treated but received prohibited concomitant medication	PP, (PK, PD)
Subject with COVID-19 diagnosis	PP (SAF, PK, PD)

Protocol deviations caused by the COVID-19 pandemic will be documented throughout the entire study. They will be assigned as a separate protocol deviation category "other" with free-text "COVID-19" and discussed during the Blinded Data Review Meeting. COVID-19 related protocol deviations will be summarized and listed separately from all other protocol deviations and will also be discussed in the CSR.

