10.1.3 Supplementary Analyses of Primary Estimand

The primary estimand described above is complemented by an additional supplementary estimand and analysis.

Only subjects in the PP Analysis Set will be included. The interest is to assess the treatment effect of CSL312 during treatment from Day 1 through Day 182 while subjects are allowed to treat HAE attacks with on-demand medications but excluding subjects who do not comply with the protocol.

The additional estimand in line with the interest of the study follows the treatment policy strategy and is described as follows:

- Treatment Condition: monthly treatment of CSL312 or placebo.
- Population: the target subject population defined by eligibility criteria, who were randomized, received at least 1 dose of CSL312 and who comply with the protocol (PP).
- Variable: time-normalized number of HAE attacks per month during treatment from Day 1 through Day 182.
- Intercurrent events: The occurrence of an intercurrent event is irrelevant. All observed values will be used regardless of occurrence of any of the following intercurrent events:

- administration of on-demand medication in addition to prophylactic treatment with CSL312,
- early study discontinuation due or not due to COVID-19.
- Population-level summary: descriptive statistics of the time-normalized number of HAE attacks during treatment from Day 1 through Day 182 by treatment.

When a subject who was at least 30 days in the treatment period after the first study drug administration discontinues study treatment due or not due to COVID-19 but stays beyond the last study drug administration in the study for more than 30 days, the HAE attacks until the last study drug administration plus 30 days thereafter will be included in the supplementary analysis of the primary estimand.

If a subject has a COVID-19 infection while participating in the study, his/her attacks will be assessed during the BDRM to determine if they might be caused/triggered by other factors, e.g. COVID-19. If there is clear evidence that they are due to the COVID-19 infection or other, they might be excluded from the analyses. Missed study drug administrations not due or due to COVID-19 or COVID-19 vaccination might also lead to the exclusion of a subject or subject's data from the supplementary analysis as well as prohibited concomitant medications due or not due to COVID-19 or COVID-19 vaccination.

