10.6 Treatment Compliance

Compliance will be summarized for the Safety Analysis Set for all injections administered during the Treatment Period.

The 1.2 mL prefilled syringes contain 200 mg garadacimab (CSL312) at a concentration of 170 mg per 1 mL. A loading does will be administered by the use of two pre-filled syringes and every subsequent dose will be administered by use of one pre-filled syringe. In eCRF only the information is collected if one or two syringes have been administered and if the full volume of the study drug for that injection was administered (Yes, No). The actual administered mL is not documented.

Technical Note: The loading dose will be treated as one injection for all calculations defined in this SAP even though the administration will require the use of two syringes and will have two kit numbers recorded in the CRF.

Thus, treatment compliance will be based on number injection with 'was the full volume of the study drug administered' answered with 'Yes' in relation to the planned number of injections.

Treatment compliance for each subject will be derived for the Treatment Period as:

$$\text{Treatment compliance (\%)} = 100 \times (\text{Number of injections with full volume administered} / \text{Total planned number of injections}),$$

with Total planned number of injection is 6 per CSP (once per month within 6-month Treatment Period).

Treatment Compliance as well as details for device malfunctions or other errors will be summarized using descriptive statistics along with further exposure data (see Section 11.1).

11 Safety Analyses

Safety data will be summarized using the Safety Analysis Set.

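### Dividing compliance by a fixed 6 flags every subject who stops before dose 5 for potential per-protocol exclusion, against a PP estimand that uses the data of early leavers

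*SAP*

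**What the plan says.** Three parts of the SAP bear on this.

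- **Section 10.6 (Treatment Compliance).** The numerator is "Number of injections with full volume administered". The denominator is fixed: "Total planned number of injection is 6 per CSP". Nothing in the section reduces it for a subject who leaves early. The two loading-dose syringes count once: "The loading dose will be treated as one injection for all calculations defined in this SAP".
- **Section 9.2, Table 9.** One row reads "Subject randomized and treated but compliance outside 80-120" (percent) and names PP, with PK and PD in brackets. The column is headed "Potential Exclusion From Analysis Set", and the blinded data review meeting settles and documents assignment to analysis sets.
- **Section 10.1.3 (supplementary PP estimand).** The population is randomized subjects who received at least one dose and complied with the protocol. Among the intercurrent events declared irrelevant, with all observed values used, is "early study discontinuation due or not due to COVID-19". The section adds that a subject at least 30 days into treatment who stops study drug but stays more than 30 days beyond the last dose contributes attacks up to 30 days after that dose. Of missed doses it says only that they might lead to exclusion.

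**The concern.** The plan separates not complying from leaving. The primary estimand (SAP 10.1.1) treats both non-compliance with treatment and early study discontinuation as irrelevant. The PP estimand drops the first from its list and keeps the second, and protocol sections 10.3.2.1 and 10.3.2.2 differ in the same way. So the PP analysis is meant to remove non-compliers and keep leavers.

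A denominator of 6 for everyone erases that distinction, because doses that never fell due are scored as doses not taken. If the flag is followed, the PP set becomes largely a set of subjects who reached dose 5. That is a post-randomization event, and agreement between PP and ITT then tells the reader less than it appears to.

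**Working it through.** **The plan's own figure.** One loading dose counted once, plus five further doses ("Subsequent doses of CSL312 will be 200 mg administered SC once monthly for 5 consecutive months (ie, Months 2 through 6"), falls on nominal Days 1, 31, 61, 91, 121 and 151: 1 + 5 = 6. The stated denominator is reproduced.

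**Compliance by number of full doses.** Compliance = 100 × full-volume injections / 6. The last column divides by the injections due while the subject was still being dosed.

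| Full doses, then stops | Fixed 6 | Within 80-120%? | Divided by doses due |
|---|---|---|---|
| 1 | 16.7% | no | 100% |
| 2 | 33.3% | no | 100% |
| 3 | 50.0% | no | 100% |
| 4 | 66.7% | no | 100% |
| 5 | 83.3% | yes | 100% |
| 6 | 100% | yes | 100% |

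The limit needs 0.8 × 6 = 4.8, so five full doses. The cut falls exactly between doses 4 and 5. The formula cannot exceed 100%, so the upper limit of 120% can never act. SAP 11.1 uses categories of below 80% and 80-100%, a further sign that threshold and formula were not aligned.

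**Treatment discontinuers who stay in the study.** On the nominal schedule, a subject who stops study drug early has a last dose numbered 1 to 5. Four of these five cases fall below 80% and are flagged for possible removal from the analysis in which 10.1.3 says their attacks will be counted.

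**Share of study leavers affected.** The documents give no dropout rate or timing. Assume, for illustration, that leaving is even over 182 days and that each leaver was fully dosed until then.

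- Leaving before Day 121: 120/182 = 66% are flagged.
- SAP 10.1 does not calculate the endpoint when observation is under 30 days, and Table 9 has a separate row for subjects without a primary efficacy assessment. For those subjects the compliance row changes nothing.
- Left over: 120 − 30 = 90 days. That is 90/182 = 49% of all leavers, or 90/(182 − 30) = 90/152 = 59% of leavers with a calculable endpoint.

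Under other timing, the share of leavers with a calculable endpoint who are flagged could be anything from 0% (all leave after a full dose 5) to 100% (all leave before it).

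**The case against.** The strongest reply is that nothing is excluded automatically. Table 9 lists potential exclusions, the PP definition in SAP 6.4 has no numeric cut-off, and the blinded meeting decides subject by subject. It can keep a fully dosed early leaver and so satisfy both sections. A reader might infer that everyone who leaves before dose 5 is excluded, or that the two rules cannot both be followed. The documents support neither; the accurate word is flagged.

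The PP estimand also restricts its population to compliers before it handles intercurrent events, and leavers after a full dose 5 pass the limit. Early discontinuation therefore keeps some meaning in that estimand. Section 10.6 itself offers the compliance figure as a Safety Set summary and does not mention PP; the link is made in Table 9. Some selection on post-randomization behaviour is inherent in any PP set.

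All of this stands and limits the point. It does not remove it. The meeting has a numeric flag pointing one way, estimand text pointing the other, and no statement of whether a dose not given because the subject had left counts as non-compliance. The meeting is blinded to arm but not to outcomes: SAP 7.1 and 10.1.3 have it assess HAE attacks in connection with COVID-19. Case-by-case decisions about leavers are better settled by a rule written beforehand.

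**Conclusion.** The point holds as an inconsistency in how potential PP exclusion is defined. Every subject who stops before dose 5 is flagged with at most 66.7% compliance, whatever their adherence while on treatment, and SAP 10.1.3 treats such subjects as usable.

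The reach is limited to the supplementary PP analysis. The primary and secondary efficacy analyses use ITT and are untouched. The number of subjects affected cannot be derived. The 49% and 59% figures rest on even leaving, full dosing until departure and nominal visit days. A reader might take 66% as the size, but that includes leavers whose endpoint is not calculated anyway. Nor are the 20 subjects randomized beyond the 40 needed a dropout forecast: the plan also gives safety data and adolescent recruitment as reasons for them.

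This should be corrected before the blinded review. It does not threaten the trial's main conclusion.

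**What to change.** For the Table 9 PP criterion, define compliance as full-volume injections divided by the injections scheduled up to the earlier of treatment discontinuation, study discontinuation and Day 151, and apply the 80% limit to that figure. Say explicitly that doses not due because of discontinuation are not non-compliance. Name both kinds of discontinuation: with study discontinuation alone, subjects who stop treatment but stay on would still be flagged. The line should also say when a dose counts as scheduled, given the ±4-day visit windows. Keep the fixed-6 figure in SAP 10.6 and 11.1 as an exposure summary.

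The new denominator is never above 6, so no subject is newly flagged. Real gaps are still caught: one dose missed or not full among 2, 3 or 4 due gives 50%, 66.7% or 75%.

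The cost is a line or two of SAP text and one extra derived variable, with no new data. The small downside is that subjects with few doses but at least 30 days of observation stay in PP, which is what 10.1.3 describes.

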11.1 Extent of Exposure

Exposure and Treatment Compliance (see [Section 10.6](#)) will be descriptively summarized by treatment arm:

- Number of SC injections received,
- Treatment Compliance (%),
- Treatment Compliance categories (<80%, 80 - 100%),
- Number of injections with not the full volume administered,
- Number of use errors,
- Number of device malfunctions by category of malfunction,
- Number of other issues.

Listings of individual subject data will present all injection records for Safety Analysis Set.

11.2 Adverse Events

AEs will be coded using the MedDRA dictionary. Treatment-emergent AEs (TEAEs), defined as AEs starting on or after the date (and time if available) of the first study drug administration, will be summarized. All AEs regardless of whether they were treatment-emergent or not will be listed.

AEs with completely or partially missing date or time will be considered treatment-emergent following the worst-case principle, unless the partial date clearly indicates that the AE started before the first administration of study drug. AEs with completely missing start dates will be considered treatment-emergent. If only the day is missing, and the start month and year of the

AE is before the start month and year of the first administration of study drug, the AE will be considered non-treatment-emergent. If day and month are missing and the start year of the AE is before the year of the first administration of study drug, the AE will be considered non-treatment-emergent.

Summaries of TEAEs will count the number of subjects, that is, subjects with multiple occurrences of the same TEAE will be counted once in the total of those experiencing this PT. Similarly, a subject with 1 or more PT in a SOC will be counted once in the total of those experiencing PTs in that SOC.

Injection site reactions (ISRs) will be summarized by SOC and PT forming a virtual SOC “Injection Site Reactions”. To decide which PTs will be considered ISRs, CSL will be provided a list in Excel format of all PTs found in the data base. CSL will review this list and mark the PTs considered ISRs in a column of this Excel sheet. The PTs summarized as ISRs will also be reported in their original MedDRA SOC. For the “Any TEAE” entry, the ISR will be reported once; they will not be counted in both their original and virtual SOC. ISRs will be presented as first “SOC” following the “Any TEAE” entry. The MedDRA SOCs and PTs will be presented in descending frequency of the overall CSL312 category. Within the same frequency, SOCs and PTs will be ordered alphabetically.

Overview summaries of TEAEs will be provided by treatment arm and total summarizing:

- Any TEAEs;
 - TEAEs related to study drug;
 - TEAEs leading to study discontinuation;
 - TEAE temporally related (onset within 24h after start of study drug administration);
 - TEAEs by severity (Mild, Moderate, Severe);
 - TEAEs by outcome (Death, Not Recovered or Not Resolved, Recovered or Resolved, Recovered or Resolved with Sequelae, Recovering or Resolving, Unknown);
 - TEAE identified as Injection Site Reaction (ISR);
 - ISRs related to study drug;
 - ISRs by severity;
- Any Serious TEAEs (SAEs);
 - SAEs related to study drug;
 - SAEs leading to study discontinuation;
 - SAE temporally related;
 - SAEs by severity (Mild, Moderate, Severe);
 - SAEs by outcome (Death, Not Recovered or Not Resolved, Recovered or Resolved, Recovered or Resolved with Sequelae, Recovering or Resolving, Unknown).

The following summary tables will be provided:

- All TEAEs by SOC and PT,
- All TEAEs leading to study discontinuation by SOC and PT,
- All TEAEs by severity and by SOC and PT,
- All TEAEs related to study drug by SOC and PT,
- All AESI by SOC and PT,
- All ISRs by SOC and PT,
- All SAEs by SOC and PT,
- All Non-serious TEAEs by SOC and PT,
- Laboratory Findings reported as AEs,
- All AEs caused by COVID-19 (see [Section 7.1](#)),
- TEAEs occurring 7 days of COVID-19 vaccine administration (see [Section 7.1](#)),
- All TEAEs excluding TEAEs occurring within 7 days of COVID-19 vaccine administration.

Summaries will include the number and percentage of subjects, the number of TEAEs, and the number of TEAEs per injection and per subject year (where applicable) derived as:

$$\text{TEAE rate per SC Injection (AERI)} = \frac{\text{Number of Events for particular SOC/PT}}{\text{Number of SC Injections}};$$

$$\text{and TEAE rate per Subject SC Year (AERS)} = \frac{\text{Number of Events for particular SOC/PT}}{\text{Subject SC years}}.$$

where subject SC years will be the sum of the time in years that subjects were exposed to study drug administered by SC injections derived as:

[date of Study Completion or date of study discontinuation [whatever is first] – the date of Study Visits Day 1 within Treatment Period +1] / 365.25.

All AEs (treatment-emergent and non treatment-emergent) will be listed including MedDRA SOC, PT and verbatim, AE start and end date:time, duration of AEs in days, intensity, serious status, relationship to study drug, outcome, action taken, and AE flags (TEAES, SAE, AESI, clinically significant laboratory finding, temporal relationship).

The following listings will be provided:

- All Non-TEAEs,
- All TEAEs,
- All TEAEs leading to study discontinuation,
- All TEAEs related to laboratory findings,
- All TEAEs caused by COVID-19,

- All SAEs,
- All SAEs with fatal outcome,
- All TEAEs occurring within 7 days of COVID-19 vaccine administration.

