9.1 Definitions

9.1.1 Adverse Event

As per the ICH Topic E2A (Clinical Safety Data Management: Definitions and Standards for Expedited Reporting), an AE is any untoward medical occurrence in a patient or clinical investigation subject administered a pharmaceutical product and which does not necessarily have a causal relationship with this treatment. An AE can, therefore, be any unfavorable and unintended sign (including an abnormal, clinically significant laboratory finding), symptom,

or disease temporally associated with the use of a medicinal (investigational) product, whether or not considered related to the medicinal (investigational) product.

The period of observation for AEs extends from the time the subject gives informed consent until the end of study (see [Section 9.4](#) for further details).

Adverse events may include:

- Exacerbation (ie, an increase in the frequency or severity) of a pre-existing condition. Illness present before study entry should be recorded in the medical history section of the eCRF and only be reported as an AE if there is an increase in the frequency or severity of the condition during the study.
- A clinical event occurring after consent but before investigational product administration.
- Intercurrent illnesses with an onset after administration of investigational product.

Adverse events do not include:

- Events identified at Screening that meet exclusion criteria.
- Medical or surgical procedures (the condition that leads to the procedure is the AE).
- Situations where an untoward medical occurrence has not taken place. For example:
 - Planned hospitalizations due to pre-existing conditions, which have not worsened.
 - Hospitalizations that occur for procedures not due to an AE (eg, cosmetic surgery).
 - Hospitalizations for a diagnostic procedure where the hospital stay is less than 24 hours in duration or for normal management procedures (eg, chemotherapy).
 - Overdose of investigational product or any concomitant therapy that does not result in any adverse signs or symptoms.

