10.3.3 Safety Analyses

Safety data will be summarized using the safety analysis set.

Adverse events with a start date and time occurring after the first administration of the study drug will be considered treatment-emergent AEs (TEAEs). Adverse events with missing or partial start date or time will also be considered TEAEs following the worst-case principle unless the partial data clearly indicates that the AE started before first administration date and time.

Treatment-emergent AEs occurring until the Follow-up Visit will be summarized. Only TEAEs will be included in analysis, although all AEs will be listed.

The following tables will be presented for AEs occurring at any dose:

- Summary of subjects with AEs (number with any AE, with AEs occurring within 24 hours of investigational product injection, with SAE, with related AE, with AEs leading to study discontinuation, with each intensity, and with each outcome).
- Summary of subjects with SAEs (number with any SAE, with SAEs occurring within 24 hours of investigational product injection, with related SAE, with SAEs leading to study discontinuation, with each intensity, and with each outcome).
- Incidence of subjects with AEs by SOC and PT.
- Incidence of subjects with SAEs by SOC and PT.
- Incidence of subjects with AEs by severity and SOC and PT.

- Incidence of subjects with AEs by relationship to investigational product and SOC and PT.
- Incidence of subjects with AEs leading to discontinuation by SOC and PT.
- Incidence of subjects with TEEs by SOC and PT.
- Incidence of subjects with bleeding events by SOC and PT.
- Incidence of subjects with severe hypersensitivity / anaphylaxis by SOC and PT.
- The number of subjects experiencing AEs which occur in at least 1 treatment in at least 1, 2, 3, 4, and 5% of events will also be presented.
- Laboratory findings reported as AEs.

Summaries will include the number and percentage of subjects, the number of AEs, and the number of AEs per injection and per subject year (where applicable).

A summary of non-serious AEs only will be presented by treatment and also by SOC, PT, and treatment.

Summaries of ISRs will be presented by treatment and also by MedDRA SOC and PT, and treatment, with relationship to investigational product and with severity.

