9.4 Prior/Concomitant Medications

Reported medications will be coded using World Health Organization Drug Dictionary Enhanced (WHO-DDE, version used will be indicated in the corresponding TLF Shells). The summary of medications will show the number and percentage of subjects taking medication displayed for Anatomical Therapeutic Chemical (ATC) class level 4 and Preferred Term. If the level 4 ATC name is not available, then the level 3 ATC name will be used and if the level 3 ATC name is not available then the level 2 ATC name will be used.

The following classification of concomitant medication related to start date of study treatment period will be applied:

- Assign to 'Prior Only' if the concomitant medication start date and end date is prior to first study treatment start date; if the subject has not taken any study treatment; or the concomitant medication start date is missing and the concomitant medication end date is before the study treatment start date;
- Assign to 'Prior and Concomitant' if the concomitant medication start date is prior to first study treatment start date and the concomitant medication end date is on or after study treatment start date or ongoing treatment;
- Assign to 'Concomitant Only' if the concomitant medication start date is on or after the first study treatment start date.

If medication start and/or stop dates are partially or completely missing, medications will be assumed to be 'Concomitant Only', unless there is clear evidence (through comparison of partial dates) to suggest that the medication started prior to the date of the first study drug administration. If there is clear evidence to suggest that the medication started prior to the date of first study drug administration (the available parts of the date are prior to the corresponding parts of the date of first study drug administration), the medication will be assumed to be 'Prior and Concomitant', unless there is clear evidence to suggest that the medication stopped prior to the date of the first study drug administration (the available parts of the medication end date are prior to the corresponding parts of the date of first study drug administration of study). If this is the case, the medication will be considered 'Prior Only'.

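### SAP 11.2 judges treatment emergence by AE start date alone, so it can count events that ended before first dose and leaves worsening of pre-dose events to an unstated recording rule

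*SAP*

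**What the plan says.** SAP 11.2 describes treatment-emergent AEs as "defined as AEs starting on or after the date (and time if available) of the first study drug administration". For incomplete dates it applies a worst-case principle: the event is treatment-emergent "unless the partial date clearly indicates that the AE started before the first administration of study drug". The two worked examples compare only the start month and year, or the start year, with first dose. For an absent start date it says "AEs with completely missing start dates will be considered treatment-emergent".

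Protocol 10.3.3 has the same rule with a slightly wider exception, "unless the partial data clearly indicates that the AE started before first administration date and time". It also settles what is tabulated: "Only TEAEs will be included in analysis, although all AEs will be listed".

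AEs are collected from informed consent (Protocol 9.4). Protocol 9.1.1 names among possible AEs "A clinical event occurring after consent but before investigational product administration". It also names an increase in frequency or severity of a pre-existing condition.

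For medications, SAP 9.4 assigns the prior-only category when "the concomitant medication start date is missing and the concomitant medication end date is before the study treatment start date".

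**The concern.** Pre-dose AE records will exist by design, because collection runs through Screening and Run-in. Two consequences follow from a rule that looks only at the start date.

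(a) A worst-case rule is meant for events whose timing is uncertain. An event with a recorded end before first dose is not uncertain, whatever is missing from its start. Counting it as treatment-emergent is a misclassification.

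(b) An event that starts in Run-in and becomes more severe or serious after first dose has a pre-dose start. If it is held as one record, the rule calls it non-treatment-emergent and the on-treatment deterioration is not counted.

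AEs, AESIs and SAEs are secondary safety endpoints, and Protocol 1.4 names thromboembolic events and bleeding as potential risks. Of the two, (b) matters more, because it could understate a safety finding.

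**Working it through.** The documents give no figure here, so the check is to apply the rule to constructed records. The inputs are the SAP 11.2 rule as written and an end-date check modelled on SAP 9.4, under which an event that ended before first dose is not treatment-emergent. First dose is set, hypothetically, at 20 June 2021.

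| Record | Start | End | SAP 11.2 as written | With end-date check |
|---|---|---|---|---|
| A | missing | 10 June 2021 | TEAE | not TEAE |
| B | June 2021, day missing | 10 June 2021 | TEAE | not TEAE |
| C | 2021 only | 10 May 2021 | TEAE | not TEAE |
| D | May 2021, day missing | 10 June 2021 | not TEAE | not TEAE |
| E | 1 June 2021, worsens 5 July, one record | 20 July 2021 | not TEAE | not TEAE |
| F | the worsening in E entered as a new AE, 5 July 2021 | 20 July 2021 | TEAE | TEAE |
| G | missing | 20 July 2021 | TEAE | TEAE |

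**Part (a).** A, B and C all ended before first dose and all count as treatment-emergent. The end-date check corrects these three. It leaves G, whose timing really is uncertain, under the worst-case rule. Nothing elsewhere rescues A to C: SAP 8.1.2 imputes no dates and refers back to 11.2. The information needed is available, since SAP 11.2 lists AE end date and time.

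**Part (b).** E and F describe the same clinical course, and the result turns entirely on how the site enters it. Protocol 9.1.1 treats exacerbation of an illness present before study entry as an AE. It separately makes an event between consent and first dose an AE from its onset. It does not say what happens when an event of the second kind worsens. Protocol 9.5 and 9.6.1 ask for an AE to be followed to resolution or stabilization, which fits a single record but does not require one. The serious-event block of the SAP 11.2 overview is defined as serious TEAEs, so a record of type E that turns serious on treatment is missing there as well.

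**The case against.** On (a), over-counting under incomplete dates is deliberate, and both documents say so. The protocol's exception speaks of partial data, and a recorded end before first dose could be read as such data. SAP section 5 declares no departure from the protocol on this point. Incomplete dates can be queried (Protocol 13.5.2), and any surviving case is visible in the listings. Most of this stands: the cases should be few and the direction is conservative. It does not remove the gap, because the SAP says partial date and its sentence on absent start dates carries no exception. A programmer following it would count record A.

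On (b), the missing recording rule is an absence from these two documents only. The eCRF and study manuals may contain it, and if sites enter worsening as a new AE the present definition already captures it. That stands, and it makes the effect conditional.

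A reader might infer that worsened Run-in events disappear from every safety table. The documents do not support that. SAP 7.1 puts all COVID-19 associated AEs in the standard tables. Several SAP 11.2 tables (AESIs, laboratory findings reported as AEs, AEs caused by COVID-19) are not titled as TEAE-only, although Protocol 10.3.3 may restrict them. All AEs, including non-TEAEs, are listed, and SAEs and AESIs are reported on an expedited basis whenever they start.

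A reader might also infer that (a) inflates the CSL312 arm. It does not single out an arm: the rule uses dates only and applies to both.

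**Conclusion.** Both gaps are real. (a) is a stated rule that gives a wrong classification in a small class of records. It goes further than a worst-case principle needs to and is out of line with SAP 9.4. Its error can only raise TEAE counts. (b) is an omission whose effect depends on site recording practice: under single-record entry, on-treatment worsening leaves the TEAE and serious-TEAE summaries but stays in the listings.

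No size can be given for either. One might be tempted to use the pre-dose share of the observation window. With 30 to 105 pre-dose days (Screening up to 30, Run-in up to 60 + 15 = 75) and 182 treatment days, that is 30/(30 + 182) = 14% to 105/(105 + 182) = 37%. At a constant event rate this is the share of AEs that start before dosing, not the share misclassified. A count of missed worsenings would need an AE rate, the fraction still ongoing at first dose, the fraction that then worsens, and the recording practice. The documents give none of these.

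**What to change.** (a) Add to SAP 11.2: *an AE whose end date/time is before the first study drug administration is not treatment-emergent, whatever is missing in the start date.* Where the end date does not settle the order of events, the worst-case rule stays.

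(b) Instruct sites, for example in the eCRF completion guidance, to enter an increase in severity or seriousness of a pre-dose AE on or after first dose as a new AE with its own start date. State in SAP 11.2 that such records are TEAEs. The site instruction does the main work. The SAP listing shows one intensity per AE and nothing in the documents shows that dated severity changes are collected, so a worsening clause in the SAP alone might not be programmable.

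The cost is two sentences in the SAP and one line of site guidance. TEAE counts may rise slightly through (b).
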